10 DEFINITION OF THE PRIMARY AND SECONDARY VARIABLES

10.1 Primary Variable(s)

The primary variables are the course of the base excess (BE) and chloride from baseline until immediately after surgery. The difference of the measurements will represent the impact of the two different volume replacement regimes on the acid base status.

The laboratory evaluation of the BE and chloride will be done using a Radiometer.

The primary variables (BE and chloride) are used for sample size calculation (see chapter 14.5).

10.2 Secondary Variables

10.2.1 Secondary Variables – Safety

Laboratory:

The analysis of blood and urine samples will be performed by the hospital laboratories according to the corresponding methods and guidelines (see Appendix 3). The reference ranges of these parameters are given in Appendix 4.

Blood samples for laboratory parameters will be taken, if not stated otherwise, at least:

- baseline i.e. prior to induction of anesthesia
- admission to ICU / IMC
- 6 hours after end of surgery
- 12 hours after end of surgery

Additional times will be listed in the context of the respective parameter.

The results of all blood analyses performed after blood sampling will be documented as follows:

- date and time of blood sampling [dd.mm.yyyy / hh:mm].

Arterial blood gas analyses

- pondus hydrogenii (pH); not temperature corrected.
- Base excess (BE) [mmol/L]
- Bicarbonate (HCO_3) [mmol/L]
- Lactate [mmol/L]
- Sodium (Na^+) [mmol/L]
- Potassium (K^+) [mmol/L]
- Calcium (Ca^{2+}) [mmol/L]
- Chloride (Cl^-) [mmol/L]
- Partial pressure of carbon dioxide (pCO_2) [mmHg]
- Partial pressure of oxygen (pO_2) [mmHg]
- Oxygen saturation (SaO_2) [%]
- Hemoglobin (Hb) [g/dL]
- Hematocrit (Hct) [%]

Hemoglobin acts as trigger for the administration of the blood products and will be monitored intraoperatively.

Additionally to the above mentioned measurements blood samples for arterial blood gas analysis will be taken intraoperatively every 15 min including recovery room every 60 minutes and additional measurements depending on the investigators decision.

Coagulation status

- Antithrombin III (AT III) [%]
- Fibrinogen [g/dL]
- Platelet count [μL]
- Activated partial thromboplastin time (aPTT) [s]

Fibrinogen, activated partial thromboplastin time (PTT), and platelet count act as trigger for the administration of the blood products and will be monitored intraoperatively.

These parameters will be recorded at baseline, at admission ICU /IMC, 6 hours and 12 hours after end of surgery.

- ROTEM (CT, MCF, LI 30)
- Platelet aggregation (TRAPtest, ASPItest, ADPtest) – only site Frankfurt am Main

These parameters will be recorded at baseline, at admission ICU /IMC, 6 hours and 12 hours after end of surgery.

Renal function

Blood samples:

- Serum creatinine (SCrea) [mg/g]
- Creatinine clearance [mL/min]
- Blood urea nitrogen (BUN) [mg/dL]
- Cystatin C [mg/L]

GFR and creatinine clearance will be calculated according to the Cockcroft-Gault Formula (see Chapter 14.1.1)

Urin samples:

Urine samples for laboratory parameters will be taken as follows:

- Amount of urine excreted (diuresis)

The urinary output will be documented intraoperatively and postoperative up to 12 hours after end of surgery:

- Start of collection; date and time [dd.mm.yyyy / hh:mm]
 - End of collection, date and time [dd.mm.yyyy / hh:mm]
 - Total collection time in hours (will be calculated afterwards)
 - Total volume of urinary output (intra- and postoperatively) in [ml]
-
- N-acetyl-beta-glucosaminidase (β -NAG) [units L⁻¹]
 - Neutrophil gelatinase-associated lipocalin (NGAL) [ng mL⁻¹]

Urin samples for the evaluation of β -NAG and NGAL will be taken in the same way as described above:

- baseline
- admission to ICU / IMC
- 6 hours after end of surgery
- 12 hours after end of surgery

Requirement of blood products

All blood products (e.g. RBC, FFP, platelets, etc.) applied according to the triggers during the study period will be documented separately for the time during surgery:

- Type [RBC, FFP, platelets or other including specification]
- Volume [mL]
- Start of administration [dd.mm.yyyy / hh:mm]
- End of administration [dd.mm.yyyy / hh:mm]
- Date of blood product [dd.mm.yyyy]
- Reason for administration (e.g. Hb, aPTT, bleeding, fibrinogen, platelet count)

The blood product documentation will be performed continuously during surgery.

Blood loss (including secretion):

The blood losses will be documented during and at end of surgery:

- Drainage blood loss; Volume [ml]
- From [dd.mm.yyyy / hh:mm]
- Through [dd.mm.yyyy / hh:mm]
- Estimated blood loss, Volume [ml]
- From [dd.mm.yyyy / hh:mm]
- Through [dd.mm.yyyy / hh:mm]

The occurrence of secondary bleeding will be documented during the whole postoperative time (i.e. starting from the end of surgery until 12 hours after end of surgery).

Adverse events

All adverse events (see chapter 11) occurring during the study period will be documented:

- Event/ symptom

- Onset of event [dd.mm.yyyy hh:mm]
- End of event [dd.mm.yyyy hh:mm]
- Intensity [mild, moderate, severe]
- Frequency [isolated, intermittent]
- Action taken [none, change in study drug dose, study drug interrupted, study drug stopped, hospitalization, concomitant therapy]
- Causal relationship to investigational product [not assessable, unlikely, possible, probable, certain]
- Serious [no, yes]
- Outcome [resolved – no sequelae; resolved with sequelae, present at final visit, death, lost to follow-up]

The adverse event documentation will be performed continuously during the study period.

10.2.2 Secondary Variables – Efficacy

Hemodynamic parameters:

- Systolic arterial pressure (SAP) [mmHg]
- Diastolic arterial pressure (DAP) [mmHg]
- Mean arterial pressure (MAP) [mmHg]
- Heart rate (HR) [beats/ min]
- Central venous pressure (CVP) [mmHg]
- Positive end-expiratory pressure (PEEP) [cmH₂O]

Please note, that a mean arterial pressure below 65 mmHg (MAP < 65 mmHg) and a central venous pressure below 10 mmHg (CVP <10 mmHg) minus PEEP are triggers for the administration of the investigational products. The crystalloid : colloid ratio is aimed intraoperatively and postoperatively 1:1. The starting infusion rate of either crystalloid or colloid is 5 ml/kg body weight (broca)/h and will be controlled by using an Infusomat.

The hemodynamic data will be measured on the contralateral site of the infusion of the investigational product.

Hemodynamic parameters will be determined:

- baseline i.e prior to induction of anesthesia
- intraoperatively every 15 min i.e. during surgery
- end of surgery i.e. wound suture
- admission to ICU / IMC
- 6 hours after end of surgery
- 12 hours after end of surgery

The documentation of the hemodynamic parameters includes the times [dd.mm.yyyy hh:mm] of assessment.

Investigational product administration:

All applied investigational product units during the study period will be documented separately for the time of administration (intra- and postoperative). The documentation of the investigational product administration will be performed continuously during the study period as follows:

- Random number
- Bottle number

- Infusion rate [mL/kg]
- Start of administration [dd.mm.yyyy / hh:mm] per infusion rate
- End of administration [dd.mm.yyyy / hh:mm] per infusion rate
- Reason for administration

The administration will be in compliance with the specified algorithm in chapter 8.2.

Drug monitoring and tolerance:

The drug tolerance will be monitored during the study period:

- Have there been any technical/ surgical problems?
[yes, no] [specification in case of 'yes'] [dd.mm.yyyyy]
- Any allergic reactions (e.g. pruritus, flush)?
[yes, no] [specification in case of 'yes'] [dd.mm.yyyyy]
- Any circulatory or respiratory problems?
[yes, no] [specification in case of 'yes'] [dd.mm.yyyyy]
- Any other clinical symptoms or adverse events?
[yes, no] [specification in case of 'yes'] [dd.mm.yyyyy]

The documentation of drug monitoring and tolerance will be performed during investigational product administration.

Concomitant medication and therapy:

All medication given during the study period including pre-anesthetic medication will be documented as follows:

- Drug, active substance
- Dose, unit and given amount (only for active substance / drug)
- Route of administration [intravenous (iv), intramuscular (im), oral (po), other]
- Start of administration [dd.mm.yyyy / hh:mm]
- End of administration [dd.mm.yyyy / hh:mm]
- Indication

All therapies performed during the study period will be documented as follows:

- Kind of therapy
- Start of therapy [dd.mm.yyyy]
- End of therapy [dd.mm.yyyy]
- Indication

Concomitant medication and therapy will be documented continuously during the study period for the time prior to anesthesia until 12 hours after surgery.

10.3 Other variables**Demographic data**

- Age [years]
- Height [cm]
- Weight [kg]
- Sex
- ASA-classification
- Apfel-Score
- Concomitant disease

- Diagnosis

Measurements:

- pe-operatively / prior to anesthesia

Surgery related data

- Kind of intervention / precise classification of surgical intervention
- Date of intervention [dd.mm.yyyy]
- Start and end of anesthetics application [hh:mm]
- Start and end of intubation [hh:mm]
- Time of incision [hh:mm]
- Time of wound suture [hh:mm]

Measurements:

- during / after surgery

Clinical Outcome

- Time on ventilator
- Ventilator settings (i.e. frequency, minute volume, ventilation pressure)

Measurements:

- measured from intubation in hours or in case of setting changes
- reintubation will be documented
- requirements of postoperative ventilatory support will be documented

- Secondary bleeding

Measurements:

- after end of surgery until 12 hours after end of surgery

- Length of stay on ICU / IMC

Measurements:

- admission to ICU / IMC
- discharge from the ICU / IMC

10.4 Source Documents

For definitions of source documents and data see section 15.

The following table represents the source documents for the data to be entered in the CRF:

Variable	Source document
Informed consent form	Informed consent form
Inclusion and exclusion criteria	Patient chart
Patient's data (demographics: sex, date of birth, weight, height, diagnosis, concomitant diseases, Apfel-Score)	Patient chart
Indication, operative measures, surgery related data	Anesthesia chart
ICU / IMC stay	Patient chart
Investigational product administration	Intraoperative and postoperative charts
Blood product administration	Patient chart
Blood loss	Patient chart

Variable	Source document
Drug monitoring and tolerance	Patient chart
Concomitant medication and therapy	Intraoperative and postoperative charts
Hemodynamics	Intraoperative and postoperative charts
Laboratory measures	Patient chart / Laboratory, device print-out
Adverse events	Intraoperative and postoperative charts, CRF, SAE-form
Clinical outcome	Patient chart
Final assessment	CRF
Study termination	CRF, patient chart

11 ASSESSING AND REPORTING OF ADVERSE EVENTS

Throughout the course of the clinical trial particular attention is paid to Adverse Events (AE) and Adverse Drug Reactions (AR).

11.1 Definitions

11.1.1 Adverse Events

An Adverse Event (AE) is any untoward medical occurrence in a patient or clinical investigation subject administered a pharmaceutical product and which does not necessarily have a causal relationship with this treatment. An AE can therefore be any unfavourable and unintended sign (including an abnormal laboratory finding), symptom, or disease temporally associated with the use of an Investigational Product, whether or not related to the investigational product or study treatment/procedures.

11.1.2 Adverse Reaction

Adverse Reactions (AR) are all untoward and unintended responses to an Investigational Product related to any application / dose administered. All adverse events judged by either the reporting investigator or the sponsor as having a reasonable causal relationship to a medicinal product qualify as AR. The expression reasonable causal relationship means to convey in general that there is evidence or argument to suggest a causal relationship.

Regarding marketed Investigational Products: a response to a product which is noxious and unintended and which occurs at applications normally used in man for prophylaxis, diagnosis, or therapy of diseases or for modification of physiological function.

11.1.3 Unexpected Adverse Reactions

An AR, the nature or severity of which is not consistent with the applicable product information (= reference document, e.g. Investigator's Brochure (IB) for an unauthorised Investigational Product or SmPC for an authorised product).

When the outcome of the AR is not consistent with the applicable product information/reference document this AR should be considered as unexpected.

The reference document is identified in section 17.8. Refer also to section 11.4.

11.1.4 Serious Adverse Event (SAE) or Serious Adverse Reaction (SAR)

Any untoward medical occurrence or effect that at any dose

- Results in death
- Is life threatening
- Requires hospitalisation or prolongation of existing inpatients' hospitalisation
- Results in persistent or significant disability or incapacity
- Is a congenital anomaly or birth defect

More than one of the above criteria can be applicable to the one event.

NOTE:

Death: is the outcome of an AE. The event to be reported comprehensively is the medical condition leading to death, e.g. underlying disease, accident.

Life-threatening: in the definition of a SAE or SAR refers to an event in which the patient was at risk of death at the time of the event; it does not refer to an event which hypothetically might have caused death if it was more severe.

Hospitalisation is defined as inpatient care of more than one calendar day (overnight admission). Admission for ambulant diagnostic procedures, overnight survey visits or ambulant visits to an emergency ward, e.g. during weekends are not considered 'hospitalisation' in the sense of the criteria for SAE / SAR, unless any of the other criteria for serious is met.

Medical judgement should be exercised in deciding whether an AE / AR is serious in other situations. Important: Aes / Ars that are not immediately life-threatening or do not result in death or hospitalisation but may jeopardise the patient or may require intervention to prevent one of the other outcomes listed in the definition above, should also be considered serious.

11.1.5 Adverse Event Intensity

Intensity	Definition
Mild	Patient is aware of signs and symptoms but they are easily tolerated
Moderate	Signs / symptoms cause sufficient discomfort to interfere with usual activities
Severe	Patient is incapable to work or perform usual activities

Cave: The term "severe" is often used to describe the intensity (severity) of a specific event. This is not the same as 'serious', which is based on patient/event outcome or action criteria (see definition 11.1.4)!

11.1.6 Adverse Event Causality

Causality code	Definition
Not assessable	A report suggesting an AE, which cannot be judged because information is insufficient or contradictory, and which cannot be supplemented or verified.
Unlikely	A clinical event, including laboratory test abnormality, with a temporal relationship, which makes a causal relationship improbable, and in which other drugs / treatments, chemicals or underlying disease(s) provide plausible explanations.
Possible	A clinical event, including laboratory test abnormality, with a reasonable temporal relationship to administration of the drug / treatment, but which also could be explained by concomitant diseases or other drugs / treatments or chemicals.
Probable	A clinical event, including laboratory test abnormality, with a reasonable temporal relationship to administration of the drug / treatment, unlikely to be attributable to concomitant disease(s) or other drugs / treatments or chemicals, and which follows a clinically reasonable response on withdrawal (dechallenge). Rechallenge information is not required to fulfil this definition.
Certain	A clinical event, including laboratory test abnormality, occurring in a plausible time relationship to study treatment and which cannot be explained by concomitant disease(s), other drugs / treatments or chemicals. The response to withdrawal of the treatment (dechallenge) should be clinically plausible. The event must be unambiguously either pharmacologically or as phenomenon, using in satisfactory rechallenge procedures if necessary.

11.2 Recording and Reporting Adverse Events and Adverse Reactions

11.2.1 Recording

The Investigator must record in detail all AEs (signs and symptoms) which are either volunteered by patients or observed during or following the course of Investigational Products administration and during the course of the study on the appropriate CRF page.

Included in the description should be

- the nature of the sign or symptom;
- the date of onset; date of resolution (duration);
- the severity / intensity (for definition see section 11.1.5);
- the investigator's judgement on possible relationship to study treatment or other therapy (for definition see section 11.1.6);
- the action taken (if any), and
- the outcome.

11.2.2 Reporting of Serious Adverse Events and Unexpected Adverse Reactions

All SAEs, whether or not deemed Investigational Product-related or expected must be reported to the Sponsor by telephone within 24 hours (one working day) of the Investigator becoming first knowledge:

Contact Name: see "Responsibilities and Addresses (section 1)

A written report must follow within five working days and is to include a full description of the event and sequelae, in the format detailed by the Serious Adverse Event reporting form provided by the Sponsor (see Appendix 3).

The Sponsor will notify the competent authorities, IECs and all investigators concerned of suspected SARs which are unexpected (SUSARs) in line with pertinent legal requirements.

While reporting adverse events, all pertinent data protection legislation must be adhered to.

Exempted from reporting within 24 hours are all SAEs which occurred before treatment with the gelatine component of the investigational regimen (bottle number 2), i.e. from induction of anesthesia until start of second bottle of investigational product treatment.

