4.3 Risk-Benefit-Assessment

The Investigational Products (IPs) Sterofundin® ISO, Gelafundin® 4% and Sodium Chloride 0.9% are registered in Germany as well as in various European countries. The proposed use of the Investigational Products in the present study is in line with the registered SmPCs. Gelofusine® Balanced is also registered in Germany since December 2011. The active substance MFG is well-known in clinical routine in order to perform volume replacement intra- and postoperatively. Gelatine solutions have been marketed for more than 40 years by now. All ingredients of the new gelatine solution are well-known and there are already comparable gelatine solutions with comparable carrier solutions on the market.

Clinical studies with other balanced volume replacement products have shown the positive impact of the balanced concept on acid base status.

Most of the proposed measures and parameters (laboratory, clinical) are performed/obtained routinely and thus do not represent major additional burden to the patient. Study specific measurements require additional blood samples of up to a maximum of 100 ml, which is considered a minimal risk to the patient.

In conclusion, the risk due to methods and measurements in the present study is considered to be low and a positive risk-benefit is assessed.

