8.2 Posology and Method of Administration

8.2.1 Dosage

Administration of the Investigational Products i.e. Gelofusine® Balanced + Sterofundin® ISO or Gelafundin® 4% + Sodium Chloride 0.9% in a blinded manner will be controlled individually by measuring CVP and MAP. The administration will be performed intravenously, starting preoperatively before induction of anesthesia. The following targets and triggers as in clinical routine apply:

The **TARGETS** for volume replacement are defined as:

- Central venous pressure between 10 and 14 mmHg (10 mmHg ≤ CVP ≤ 14 mmHg) minus PEEP after treatment with vasoactive agent

and

- Mean arterial pressure greater than 65 mmHg (MAP > 65 mmHg)

TRIGGERS for infusion of gelatines during surgery and postoperatively are:

- Central venous pressure (CVP) < 10 mm Hg minus PEEP

and

- Mean arterial pressure (MAP) < 65 mm Hg

The crystalloid : colloid ratio is 1 : 1 intra- and postoperatively. The first bottle is the crystalloid followed by the colloid and alternating thereafter. The starting infusion rate of either crystalloid or colloid is 5 mL/kg body weight (broca)/h and will be controlled by using an Infusomat.

The above specifications for crystalloid : colloid ratio and infusion rates are recommendations that ought to be met. However, the rates have to be adjusted according to the individual patient's need as defined by the above targets and triggers, up to a maximum of 5 mL/kg body weight (broca)/h for the crystalloids and of 20 mL/kg body weight (broca)/h for the colloids, as considered necessary by the investigator to stabilize the hemodynamics.

Postoperatively the investigational products will be given according to the patient's need.

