- Immediate stop of infusion as soon as there are any signs of adverse reactions.

Emergency treatment of anaphylactoid reactions follows established schedules, depending on the severity of the reaction. It cannot be predicted by any test procedure which patients are likely to experience anaphylactoid reactions, nor is it possible to foresee the course and severity of any such reaction.

Anaphylactoid reactions caused by gelatin solutions may either be histamine mediated or histamine independent. Histamine release can be prevented by the use of a combination of H1- and H2 receptor blockers.

Prophylactic administration of corticosteroids has not proven effective.

Adverse reactions may occur in conscious and anesthetized patients. In the acute phase of volume deficiency shocks so far no anaphylactoid reaction has ever been reported.

Sterofundin® ISO:

Overdose or too fast administration may lead to water and electrolyte (including acetate, malate) overload with respective signs and symptoms as described in SmPC section "Overdose".

Gastrointestinal disorders:

Rare: Although oral magnesium salts stimulate peristalsis, paralytic ileus has been rarely reported after intravenous infusion of magnesium sulphate.

General disorders and administration site conditions:

Adverse reactions may be associated with the technique of administration including febrile response, infection at the site of injection, local pain or reaction, vein irritation, venous thrombosis or phlebitis extending from the site of injection and extravasation.

Immune system disorders

Not known: Hypersensitivity reactions characterized by urticaria have been occasionally described after the intravenous administration of magnesium salts.

Sodium Chloride 0.9%:

Overdose may result in hypernatremia, hyperchloremia, overhydration, hyperosmolality of the serum, and metabolic acidosis.

Administration of larger amounts may lead to hypernatremia and hyperchloremia (see also SmPC section "Overdose").

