11.5 Pregnancies

Not applicable, because the study is performed in the operation room and the ICU / IMC.

12 STUDY SCHEDULE**12.1 Procedures at Each Visit**

Pre-operatively:

- Verification of inclusion and exclusion criteria, including informed consent
- Blood samples for laboratory evaluation of electrolyte and coagulation status
- Urine sample in women of child bearing potential for pregnancy testing
- Demographic data, history
- Apfel-Score
- Pre-operative medication / therapy as medically indicated and standardized (including pre-operative fasting time)

Pre-anesthesia:

- Randomization (i.e. supply of blinded study samples)
- Set of catheters (e.g. arterial / central venous catheter)
- Baseline laboratory and hemodynamics
- Blood sampling for baseline laboratory evaluation
- Baseline ROTEM and baseline platelet aggregation
- Administration of first bottle of investigational products, i.e. crystalloid component
- Drug monitoring and tolerance
- Induction of anesthesia
- Concomitant medication and therapy (including concomitant medication and therapy prior induction of anesthesia; including blood products acc. to trigger)
- Adverse events/ reactions

After induction of anesthesia/prior surgery :

- Administration of investigational products
- Time on ventilator
- Final positioning of patient in operating theatre
- Set of urinary catheter for urine sampling
- Hemodynamics
- Blood sampling for laboratory evaluation
- Drug monitoring and tolerance
- Concomitant medication and therapy (including concomitant medication and therapy prior induction of anesthesia; including blood products acc. to trigger)
- Adverse events / reactions

During surgery :

- Administration of investigational products for volume replacement
- Surgery related data
- Intraoperative hemodynamics (every 15 min; CVP minus PEEP and MAP serve as trigger for IP-administration)
- Blood sampling for laboratory evaluation (blood gas analysis every 15 minutes, recovery room hourly)
- Drug monitoring and tolerance
- Recording of blood loss (drainage blood loss and estimated blood loss)
- if applicable, blood product administration
- Time on ventilation
- Concomitant medication and therapy
- Adverse events / reactions

End of surgery:

- Administration of investigational products for volume replacement according to algorithm
- Surgery related data
- Hemodynamics
- Blood sampling for laboratory evaluation
- Drug monitoring and tolerance

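### The exemption from 24-hour SAE reporting before bottle 2 covers time on a randomised investigational product, and its start and end are not clearly defined

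*Protocol*

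**What the plan says.** Protocol section 11.2.2 opens with a rule that does not depend on causality or expectedness: "All SAEs, whether or not deemed Investigational Product-related or expected must be reported to the Sponsor by telephone within 24 hours (one working day"). A second step is set for paper: "A written report must follow within five working days". The section closes with the exception: "Exempted from reporting within 24 hours are all SAEs which occurred before treatment with the gelatine component of the investigational regimen (bottle number 2"), which it then explains as the period "from induction of anesthesia until start of second bottle of investigational product treatment".

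Other sections say what bottle 1 is. Section 8.2.1: "The first bottle is the crystalloid followed by the colloid and alternating thereafter". Section 8.3 gives odd numbers to the crystalloid of the allocated regimen and even numbers to the colloid. The pre-anaesthesia list in section 12.1 puts randomisation first, later "Administration of first bottle of investigational products, i.e. crystalloid component", and only after that induction. Section 4.3 counts both crystalloids among the products under investigation (the sentence begins "The Investigational Products (IPs) Sterofundin" and goes on to include sodium chloride 0.9%). Section 11.4 lists a reaction for the test-arm crystalloid: "Hypersensitivity reactions characterized by urticaria have been occasionally described after the intravenous administration of magnesium salts".

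**The concern.** The exception is written as if exposure to study treatment began with the gelatine. In this trial the comparison is between two regimens, each made of a crystalloid and a colloid, and exposure begins with the crystalloid. The exempt period therefore includes time on a randomised, blinded product, and the exception draws no line between an event attributed to anaesthesia and one attributed to bottle 1.

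At stake is how soon the sponsor hears of a suspected serious reaction to one of the crystalloids. The sponsor's duty to notify unexpected serious reactions, also in section 11.2.2, can only be met once the sponsor has been told. Section 17.8 makes the SmPCs of all the investigational products the reference for expectedness, so the protocol's safety framework covers the crystalloids, while the fast reporting route is switched off for the first of them. Every patient who starts treatment passes through this period.

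**Working it through.** The protocol states no figure that has to be reproduced. The check sets the text side by side, with some arithmetic for scale.

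**1. Is bottle 1 randomised study treatment?** Yes. It is arm-specific (8.3), named as investigational product (4.3, 12.1), supplied blinded after randomisation (12.1), and marks the start of treatment (8.2.3, 13.1).

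**2. When does the exemption start?** The main clause covers everything before gelatine, which takes in bottle 1 before induction. The explanatory clause starts only at induction. Since bottle 1 starts before induction (8.2.3, 12.1), the two clauses treat the first part of exposure differently: exempt under one, under the 24-hour rule under the other.

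**3. When does it end?** At the start of bottle 2. That is not a fixed time: section 8.2.1 ties gelatine infusion to CVP and MAP triggers and calls the 1:1 ratio a recommendation. If treatment ends during bottle 1, for example because of a serious reaction to it, bottle 2 never starts and, read literally, the exemption has no end for that patient.

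**4. How long is bottle 1?** Inputs: 500 mL per bottle (8.1.3); 5 mL/kg Broca weight per hour, both the starting and the maximum crystalloid rate (8.2.1); Broca weight = height in cm − 100 (section 2). The heights are assumed, as the protocol gives none.

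Duration in hours = 500 / (5 × Broca weight)

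| Assumed height (cm) | Broca weight (kg) | Rate (mL/h) | Duration (h) |
|---|---|---|---|
| 150 | 50 | 250 | 2.00 |
| 160 | 60 | 300 | 1.67 |
| 170 | 70 | 350 | 1.43 |
| 180 | 80 | 400 | 1.25 |
| 190 | 90 | 450 | 1.11 |

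This is the nominal length of the whole bottle. A slower rate lengthens it, and an early start of the colloid shortens the time before bottle 2. The part before induction is exempt only on the wider reading.

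**5. What reporting remains?** Section 11.2.1 still requires every AE on the CRF with a causality judgement, and the schedule in section 12.2 records SAEs continuously from before induction. The exception names only the 24-hour call. Whether the written report still applies is unclear, because it is described as following that call. If it applies, the delay is up to five working days. If only the CRF applies, section 17.9 allows up to two weeks after the patient completes.

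**6. What does such a delay mean for the trial?** Planned recruitment is 64 patients in one year (13.2): 64 / 52 ≈ 1.2 per week. A lag of about one week spans about one further patient, and two weeks about 2 × 1.23 ≈ 2.5. The study-level stopping rule in section 7.4.1 acts at 7 patients (0.10 × 64 = 6.4, rounded up).

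**The case against.** The strongest reply is that an explicit exception to a general rule is a choice rather than a contradiction. The period coincides with propofol, fentanyl, rocuronium and peridural dosing (section 9), and the sponsor may have wanted to avoid expedited reports of anaesthesia effects. That is plausible, but no reason is given, and an exception defined by a time window cannot separate the two causes when induction drugs and bottle 1 overlap. Nor does registration of the crystalloids explain the different treatment, since section 4.3 says that both gelatines are registered too.

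Other parts of the reply do stand. A reader might infer that these events escape safety review or never reach the sponsor. The documents do not support that: only the telephone call is waived, and CRF recording and the sponsor's notification duty remain. A reader might also infer that unexpected serious reactions would be notified too late. The protocol gives no notification deadline of its own, so this cannot be shown. The urticarial reaction in section 11.4 comes from the product information and would count as expected unless its nature, severity or outcome differed; for sodium chloride 0.9% that section lists only effects of overdose or large volumes. Finally, a reader might infer that the stopping rule is compromised. Of the events that it singles out, mainly anaphylaxis is plausible so early, the lag spans one to three patients, and section 7.4.1 does not tie its count to the 24-hour call. The absence of a DSMB adds little, because the board described in section 17.1.3 would review accumulating data and not take individual calls.

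**Conclusion.** The point holds as a should-fix. Followed as written, section 11.2.2 delays the report of a suspected serious reaction to a randomised product during the post-induction part of bottle 1. The exception contradicts itself on when it begins and is open-ended if bottle 2 is not given.

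The size is modest. The whole bottle lasts about 1.1 to 2.0 hours under the assumed Broca weights of 90 to 50 kg at 5 mL/kg/h, with bottle 2 following a completed bottle 1. It would overstate the point to call all of that time exempt: only the part after induction clearly is, and the protocol does not say how long that part lasts. The delay is up to five working days, or up to two weeks after patient completion, depending on whether the written report survives. The primary endpoints, error rate, sample size and analysis sets are not affected.

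A minor wording matter sits in the same section. The call is due within 24 hours, glossed as one working day, and these differ at weekends: an event learned of on a Friday afternoon is due on Saturday by one and on Monday by the other.

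**What to change.** Delete the exemption and state in section 11.2.2 that every SAE from the start of bottle 1 falls under both the 24-hour call and the five-working-day written report. This removes the unclear start and the missing end together. Moving the end of the exemption to the start of bottle 1 is not a separate option under the explanatory clause: the window would open at induction, after it had already closed. As a minor edit, replace the double deadline for the call by a single one.

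The cost is amendment wording, a notice to the two sites, and a few more expedited reports of events that turn out to be anaesthesia-related. Treatment, endpoints and sample size stay as they are.
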